6.4 Prior and Concomitant Therapy

Prior therapies include systemic therapies, radiation, and surgeries.

Any concomitant therapy given for a study protocol related AE should be recorded from Cycle 1 Day 1 of study treatment through the Safety Follow-Up Visit.

6.4.1 Required Prior or Concomitant Therapy

Subjects must have received four cycles of platinum-etoposide and three or four cycles of ICI immediately prior to study enrollment (for details, see Section 5.0).

6.4.2 Allowed Concomitant Therapy

Standard supportive care measures for symptom control or drug related toxicity are allowed, such as analgesics, antiemetics, electrolyte replacement, and hydration. Other prescribed medications for non-neoplastic conditions are allowed, as well as vitamins and nutritional or herbal supplements, which must be recorded in the medication list.

Concomitant corticosteroids (prednisone or equivalent) may be used at a dose of ≤ 10 mg/day. The use of intermittent high dose corticosteroid treatment to prevent or manage hypersensitivity reactions or other noncancer-related symptoms is allowed (including premedication for known hypersensitivity reactions to contrast material for imaging scans).

Routine prophylaxis with vaccines is permitted, excluding those containing live microorganisms.

If the subject is taking chronic suppressive anti-infectives (e.g., antiviral, antifungal, or antibacterial), appropriate evaluation must be completed prior to registration, and documentation must exclude active infection. The subject should continue suppressive anti-infectives for the duration of study participation.

Birth control or contraceptive measures are allowed.

6.4.3 Prohibited Concomitant Therapy

Subjects are prohibited from receiving the following therapies during trial participation:

1. Any other systemic anti-cancer therapy, including chemotherapy, immunotherapy, or biologic therapy not specified in this protocol.
2. Any investigational agents not specified in this protocol.
3. Monoamine oxidase A and B inhibitors (MAOIs).
4. All hematopoietic growth factors: romiplostim, eltrombopag, granulocyte and granulocyte-macrophage colony stimulating factor (G-CSF and GM-CSF) and erythropoietin (EPO).
5. Systemic corticosteroids at a dose of > 10 mg/d (prednisone equivalent).

Note: The use of intermittent high dose corticosteroid treatment to prevent or manage hypersensitivity reactions or other symptoms not related to cancer is allowed (including premedication for known hypersensitivity reactions to contrast material for imaging scans).

6. Radiation therapy, including prophylactic cranial irradiation and consolidative thoracic radiation therapy. Note that radiation therapy for isolated CNS progression is allowed, during which time bomedemstat should be held (see Section 8.2.7.1).
7. Live vaccines within 30 days prior to the first dose of trial treatment and while participating in the trial. Examples of live vaccines include, but are not limited to, the following: measles, mumps, rubella, chicken pox, yellow fever, rabies, BCG, and typhoid (oral) vaccine. Seasonal influenza vaccines for injection are generally killed virus vaccines and are allowed; however, intranasal influenza vaccines (e.g. Flu-Mist®) are live-attenuated vaccines and are not allowed.
8. Subjects are specifically prohibited from receiving the following therapies while the platelet count is $< 50 \times 10^3/\text{mCL}$:
 - a. Non-steroidal anti-inflammatory medications with COX-1 inhibitory/antiplatelet activity (e.g. aspirin, ibuprofen, naproxen, etc.).

- b. Antiplatelet agents, e.g. clopidogrel, prasugrel, ticagrelor, ticlopidine.
- c. Anticoagulation with warfarin, Factor Xa inhibitors (e.g. apixaban, edoxaban, rivaroxaban), direct thrombin inhibitors (e.g. dabigatran), or low molecular weight heparins (enoxaparin, dalteparin).

6.5 Supportive Care Guidelines

Subjects should receive appropriate supportive care measures as deemed necessary by the treating investigator including but not limited to the items outlined below:

1. Anti-infectives: Subjects with a documented infectious complication should receive oral or IV antibiotics or other anti-infective agents as considered appropriate by the treating investigator for a given infectious condition, according to standard institutional practice.
2. Immune-related adverse events: Immune-related adverse events should be managed in keeping with institutional and national guidelines⁴⁷.
3. Infusion reactions while receiving atezolizumab: Acute infusion reactions should be managed according to institutional guidelines.
4. Transfusions: transfusions of red blood cells and platelets are at the discretion of the investigator and should be performed in accordance with institutional guidelines. Prophylactic transfusion of platelets when the platelet count is < 10x10³/mCL is strongly encouraged.

6.6 Discontinuation of Study Treatment and/or Withdrawal from Study for Individual Subjects

Specific criteria for discontinuation of study treatment and/or withdrawal from study are listed in Sections 6.6.1 (disease progression) and 6.6.2 (other reasons).

Subjects may withdraw consent at any time for any reason or be withdrawn from the trial at the discretion of the investigator should any untoward effect occur. In addition, a subject may be withdrawn by the investigator or the Sponsor if enrollment into the trial is inappropriate, the trial plan is violated, or for administrative and/or other safety reasons.

Subjects who meet criteria to discontinue study treatment will be converted to Off Treatment status and will be followed per the Study Calendar (Section 7.0) via the End of Treatment Visit and Survival Follow-up assessments (see Section 8.5.3), including the collection of any protocol-specified blood specimens, unless consent is withdrawn, or the subject is lost to follow-up or enrolled in another clinical study.

Subjects who discontinue study treatment for a reason other than disease progression and have not initiated other anti-cancer therapy will be followed with Monitoring assessments (Section 8.5.3.3).

All subjects will be followed for survival. Subjects who decline to return to the site for evaluations will be offered follow-up by phone every 3 months as an alternative.

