3.1.6 Missed Doses

Patients who do not take their bomedemstat dose at the usual required time should take it immediately upon noting that it was not taken; however, the patient should not take the dose more than 12 hours after the usual dosing time. If a patient misses a dose, they should not take two doses the following day, but should notify their study coordinator and continue with their normal daily dose the following day.

For a dosing hiatus due to a serious adverse event (SAE), please consult the Principal Investigator for guidance on dosing re-start. Patients who miss an extended number of bomedemstat doses or exhibit serial non-compliance with treatment may be removed from the study at the discretion of the Principal Investigator.

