8.5.3.3 Monitoring

Subjects who discontinue study treatment for a reason other than disease progression or withdrawal from study move into the monitoring phase and should be assessed radiographically every 8 weeks (56 ± 7 days) as in Section 8.2.7 to monitor disease status. Every effort will be made to collect information regarding disease status until the start of new anti-neoplastic therapy, disease progression, death, or end of the study. Information regarding post-study anti-neoplastic treatment will be collected if new treatment is initiated.

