8.5.3.4 Survival Follow-up

Once a subject is no longer eligible for study treatment due to disease progression or starts a new anti-cancer therapy outside the confines of this study, the subject moves into the survival follow-up phase. Survival status of the subject will be ascertained every 12 weeks, via medical records or by directly contacting the patient, until death, withdrawal of consent, or the end of the study, whichever occurs first. Three attempts to contact a subject should be made before the subject is considered lost to follow up.

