9.7 Overall Survival (OS)

Measured from the date of registration until death from any cause. OS for participants last known to be alive is censored at the date of last contact.

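### Section 6.6 excepts subjects who join another clinical study from Survival Follow-up, against its own closing paragraph and Sections 6.1 and 8.5.3.4; the wording should be reconciled (minor)

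*Combined protocol and SAP*

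**What the plan says.** **Section 6.6, third paragraph.** Subjects who stop treatment are followed "via the End of Treatment Visit and Survival Follow-up assessments (see Section 8.5.3), including the collection of any protocol-specified blood specimens". The same sentence then sets the exception: this holds "unless consent is withdrawn, or the subject is lost to follow-up or enrolled in another clinical study". Survival Follow-up is thus named in the sentence that carries the exception.

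**Section 6.6, last paragraph.** "All subjects will be followed for survival". Telephone follow-up is offered to those who decline to return to the site.

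**Section 6.1.** After progression or new anticancer treatment, subjects are followed for survival until they die or the study terminates.

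**Section 8.5.3.4.** A subject who is no longer eligible for treatment because of progression, or who "starts a new anti-cancer therapy outside the confines of this study, the subject moves into the survival follow-up phase". Status is obtained every 12 weeks from medical records or by contact, "until death, withdrawal of consent, or the end of the study, whichever occurs first". Three contact attempts come before a subject counts as lost. Joining another study is not among the reasons to stop.

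**OS analysis.** OS is the only secondary objective (1.2). It is estimated by Kaplan-Meier (10.3), and "OS for participants last known to be alive is censored at the date of last contact" (9.7). No OS hypothesis, threshold or power is given.

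**Non-compliance.** Section 3.1.6 says "Patients who miss an extended number of bomedemstat doses or exhibit serial non-compliance with treatment may be removed from the study", at the Principal Investigator's discretion; 3.2.6 repeats this. Section 6.6.2, items 4 and 9, sends non-compliant subjects to Off Treatment monitoring. Section 8.5.3.3 reads: "Subjects who discontinue study treatment for a reason other than disease progression or withdrawal from study move into the monitoring phase".

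**The concern.** One event, entry into another trial after progression, starts survival follow-up under 8.5.3.4 if it brings new therapy, yet ends it under the exception in 6.6. Section 2.1 describes progression as near-universal and later options as limited, so such entry is foreseeable, although the documents do not say how common it is.

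A site that followed the exception would stop survival contact when the patient joined, and 9.7 would censor the patient as alive at that date. Kaplan-Meier assumes that censored patients have the same later hazard as those still at risk. Patients censored just after progression will often have a higher hazard than the rest of the risk set, part of which has not progressed. Patients fit enough for another trial may have a lower hazard than other patients who have progressed. The two effects pull in opposite directions.

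The non-compliance wording raises a smaller question: whether a removed patient still has disease-status scans and survival follow-up.

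**Working it through.** **1. The passages side by side**

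| Place | Does joining another study end survival follow-up? |
|---|---|
| 6.6, third paragraph | Yes, on its plain reading |
| 6.6, last paragraph | No: all subjects are followed |
| 6.1 | No: until death or study termination |
| 8.5.3.4 | No: not listed as an end; new outside therapy is a start |

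**2. The plan's own precision figure.** Section 10.3 says proportions are estimated to within 17% with 34 patients. Check: 1.96 × √(0.5 × 0.5 / 34) = 0.168. It reproduces. The plan gives no OS figure to reproduce. The stated 90% power concerns 6-month progression-free survival (PFS); with 17 of 34 as the threshold the exact binomial value is 0.913, and it does not depend on this clause.

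**3. Illustration if the exception is applied.** Only the 35% 6-month PFS comes from the documents (10.3). The rest is assumed: exponential PFS; exponential survival after progression with a median of 5 months; a share of patients joins another trial and is censored one month after progression if still alive; everyone else is followed to death.

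- Progression hazard: λ = -ln(0.35)/6 = 0.1750 per month.
- Post-progression hazard: μ = ln(2)/5 = 0.1386 per month.
- True 12-month OS: [λ·exp(-12μ) - μ·exp(-12λ)] / (λ - μ) = (0.1750 × 0.1895 - 0.1386 × 0.1225) / 0.0363 = 0.445.

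The Kaplan-Meier value with censoring comes from a large simulation, good to about 0.1 point:

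| Share joining | True 12-month OS | Kaplan-Meier reads | Shift (points) |
|---|---|---|---|
| 10% | 44.5% | 45.9% | +1.4 |
| 20% | 44.5% | 47.3% | +2.8 |
| 30% | 44.5% | 48.9% | about +4.5 |

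At 30% joining, the median reads 11.8 instead of 10.8 months. Deaths observed: a joiner is alive one month after progression with probability exp(-0.1386) = 0.871, so 34 × (1 - 0.3 × 0.871) ≈ 25 of 34.

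**4. Sensitivity to prognosis at 30% joining**

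| Post-progression median, joiners / others | True 12-month OS | Kaplan-Meier reads | Shift (points) |
|---|---|---|---|
| 5 / 5 months | 44.4% (simulated) | 48.9% | +4.5 |
| 6 / 4 months | 41.7% | 44.0% | +2.3 |
| 8 / 4 months | 44.2% | 44.4% | +0.2 |

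**5. Wider assumptions.** A second set censors at progression itself, lets only the fitter half join (0 to 40% of all patients), takes 6-month PFS as 35% or 60%, and sets post-progression medians at 5/5, 8/4 or 10/3 months (fitter/other). The shift then runs from -1.0 to +9.6 points. It is negative only with the 10/3 medians and 35% PFS. Even the sign is therefore open.

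**The case against.** The strongest reply is that the protocol taken as a whole keeps survival follow-up going. Three passages say so, one of them in 6.6 itself. Another is 8.5.3.4, part of the section to which the exception sentence refers. Status may come from medical records, so a site would have to ignore all three to stop. The exception could also be read as limiting only visits and blood specimens. Most of this stands and sets the severity. The narrow reading is strained, however: withdrawal of consent and loss to follow-up are in the same list and naturally govern all follow-up. The conflict remains.

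A reader might infer that OS will be biased. The documents do not support that. Bias requires a site to apply the exception and enough patients to join. The joining shares and post-progression survival used above are assumptions, and the results include near zero. The count of 25 observed deaths also assumes no administrative censoring. OS is untested, and every shift shown is smaller than the 17-point precision.

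A reader might also infer that primary-endpoint data are lost when patients are removed for non-compliance. That is not shown. Sections 3.1.6 and 3.2.6 say only that removal may happen and do not say that follow-up stops, and 6.6.2 sends such subjects to monitoring. The open question is whether removal counts as the study withdrawal that 8.5.3.3 excludes from Monitoring. This is an ambiguity, not a contradiction.

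**Conclusion.** The text conflict in 6.6, and between 6.6 and Sections 6.1 and 8.5.3.4, is established by reading alone. Its effect on OS is conditional. If the exception is applied, assumed joining shares of 10% to 30% shift 12-month OS by about zero to +4.5 points, and broader assumptions give about -1 to +10. Neither size nor sign can be obtained from the documents. Sample size, power and the primary test are unaffected. Severity is minor: the edit is worth making because it is simple and keeps deaths after entry into another trial in the OS estimate. The non-compliance wording is a secondary clarification.

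**What to change.** In 6.6, state that enrolment in another clinical study may end study visits and specimen collection but does not end survival ascertainment, which continues under 8.5.3.4 from records or by contact.

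Reconcile the removal wording in 3.1.6 and 3.2.6 with 6.6.2, items 4 and 9, and with 8.5.3.3, so that it is clear whether disease-status scans and survival follow-up continue for non-compliant subjects.

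The cost is protocol wording only. Survival status is already collected every 12 weeks by these means, so the 6.6 change adds no visits.

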6.6.1 Disease progression

Confirmed radiographic disease progression per RECIST 1.1 (Section 9.2.4) renders a subject ineligible for further study treatment, except that isolated CNS progression does not require permanent study treatment discontinuation (see Section 8.2.7.1 for further detail).

In the event of unconfirmed disease progression, study treatment can be continued until disease progression is confirmed (see Section 8.2.7.2 for further detail).

6.6.2 Other criteria for discontinuation of study treatment and/or withdrawal

An individual subject will not receive any further study treatment and will proceed to Off Treatment monitoring if any of the following occur in the subject in question:

1. The subject withdraws consent.
2. Unacceptable adverse events as defined in Section 6.3.

Note that encephalopathy of any grade is always considered an unacceptable adverse event (see Section 10.2.1).

3. Adverse event that, in the opinion of the investigator, contraindicates further dosing.
4. Subject noncompliance that, in the opinion of the investigator, warrants withdrawal, e.g., refusal to adhere to scheduled visits.
5. Subject is determined to have met one or more of the exclusion criteria for study participation at study entry and continuing investigational therapy might constitute a safety risk.
6. Intercurrent illness that prevents further administration of treatment.
7. Investigator's decision to withdraw the subject.
8. The subject has a confirmed positive serum pregnancy test.
9. Noncompliance with trial treatment or procedure requirements.
10. The subject is lost to follow-up.
11. Grade ≥ 3 infusion reaction.

7.0 STUDY CALENDAR

Title/Cycle	Screening	On Treatment 21 Day Cycles				Off Treatment			Survival Follow-Up
		Every Treatment Cycle				End of Treatment	Monitoring	Safety Follow-Up	
Timing	Day -28 to 1	Day 1	Day 8	Day 15	Within 7 days of Day 1 of next cycle	Time of discontin.	~Q8w	30d after discontinuation of study treatment	~Q12w
Window (days)	-	+/- 2 (subseq. cycles)	+/- 2	+/- 2		+ 7	+/- 7		
Informed Consent	X								
Inclusion / Exclusion Criteria	X								
Demographics / Medical History / Prior and Concomitant Medication Review	X								
Bomedemstat Administration ¹		Daily	—	→					
Atezolizumab Administration ²		X							
Survival Status									X
Adverse Event / Concomitant Medication Review ³		X ³				X	X	X	
Full Physical Examination	X								
Directed Physical Examination ³		X ³				X	X	X	
Vital Signs and Weight	X	X				X	X	X	
ECOG Performance Status	X	X				X	X	X	
Pregnancy Test	X								
Complete Blood Count with Differential (CBC w/ Diff) ⁴	X	X	X ⁴	X ⁴		X	X	X	
Comprehensive Serum Chemistry Panel	X	X				X	X	X	
PT/INR and aPTT	X								
Serum cortisol, FT4, TSH		X							
Archival tissue collection	X								
Blood for correlative research	X	X				X	X		
Disease/response assessment ⁵	X ⁵				X ⁵		X ⁵		

1. Bomedemstat is taken daily. All doses are self-administered by the patient off-site.

2. Atezolizumab is administered in the clinic as an IV infusion. There are no specific restrictions regarding timing relative to the patient's bomedemstat dose.

3. Note that, during On Treatment status, provider visits (to facilitate AE/concomitant medication review and physical examination) are only required on Day 1 of each treatment cycle. Visits on other cycle days, including Day 8 and Day 15, can be performed if clinically necessary but are not mandated.

4. Weekly CBC w/ diff required throughout Cycle 1. After Cycle 1, CBC w/ diff should be performed weekly until the patient has not required a bomedemstat dose modification or hold for at least 28 days, at which point CBC w/ diff can be spaced out to no less frequently than every 14+/-2 days. If a dose modification is subsequently required, weekly CBC w/ diff should resume until at least 28 days have elapsed without need for a dose modification or hold, at which point CBC w/ diff can again be spaced out to no less frequently than every 14+/-2 days.

Version 3.0 August 08, 2022

5. Disease/response assessment during the screening period may have been performed up to 14 days prior to initiation of study treatment. Disease response assessments will occur every 6 weeks. After completion of 24 weeks of study treatment, the intervals can be extended to up to 9 weeks +/- 7 days. CT scans should encompass at least the chest and abdomen. CT pelvis should be included according to usual clinical practice. For patients who are known to have CNS disease at the time of study enrollment, monitoring of the CNS should proceed according to usual clinical practice.

8.0 STUDY PROCEDURES AND ASSESSMENTS

The Study Calendar (Section 7.0) summarizes the study procedures to be performed at each visit. Individual study procedures are described in detail below. It may be necessary to perform these procedures at unscheduled time points if deemed clinically necessary by the investigator.

8.1 Subject Enrollment

8.1.1 Informed Consent

The Investigator must obtain documented consent from each potential subject prior to participating in the study.

Consent must be documented by the subject's dated signature on a consent form along with the dated signature of the person conducting the consent discussion.

A copy of the signed and dated consent form should be given to the subject before participation in the trial per Institutional Standards.

The initial informed consent form, any subsequent revised written informed consent form and any written information provided to the subject must receive the IRB/ERC's approval/favorable opinion in advance of use. The subject should be informed in a timely manner if new information becomes available that may be relevant to the subject's willingness to continue participation in the trial. The communication of this information will be provided and documented via a revised consent form or addendum to the original consent form that captures the subject's dated signature.

The informed consent will adhere to IRB/ERC requirements, applicable laws and regulations and Sponsor requirements.

8.1.2 Inclusion/Exclusion Criteria

All inclusion and exclusion criteria will be reviewed by the investigator or qualified designee to ensure that the subject qualifies for the trial.

8.1.3 Medical History

A medical history will be obtained by the investigator or qualified designee. Medical history will include all active conditions, and any condition diagnosed within the prior 10 years that is considered clinically significant by the Investigator. Details regarding the disease for which the subject has enrolled in this study will be recorded separately and not listed as medical history.

8.1.4 Prior and Concomitant Medications Review

The investigator or qualified designee will review prior medication use, including any protocol-specified washout requirement.

8.1.5 Disease Details

The investigator or qualified designee will obtain prior and current details regarding disease status.

